2.14.10.2 Temporary Discontinuation

Treatment should be withheld temporarily if any of the following conditions apply:

- Occurrence of hypersensitivity after instillation of the eye drops
- Rechallenge can be considered at the discretion of the investigator in consultation with the medical monitor

The investigator may decide to temporarily discontinue treatment for other reasons if deemed appropriate for the safety and well-being of the participant. The medical monitor should be informed.

2.14.11 *Participant Discontinuation / Withdrawal from the Study*

A participant may withdraw from the study at any time at his/her own request or may be withdrawn at any time at the discretion of the investigator for safety, behavioral, or compliance reasons. This includes cases in which, in the investigator's opinion, continued participation in the study would be harmful to the participant's well-being. This is expected to be uncommon.

- At the time of discontinuing from the study, if possible, the final study visit should be conducted as early discontinuation visit, followed by safety follow-up as determined by the investigator in keeping with standard of care. See SoA for data to be collected at the time of study discontinuation and follow-up and for any further evaluations that need to be completed.
- The participant will be permanently discontinued both from the study intervention and from the study at that time.
- If the participant withdraws consent for disclosure of future information, the Sponsor may retain and continue to use any data collected before such a withdrawal of consent.

2.14.12 *Lost to Follow-up*

A participant will be considered lost to follow-up if he or she repeatedly fails to return for scheduled visits and is unable to be contacted by the study site.

The following actions must be taken if a participant fails to return to the clinic for a required study visit:

- The site must attempt to contact the participant and reschedule the missed visit as soon as possible, counsel the participant on the importance of maintaining the assigned visit schedule, and ascertain whether or not the participant wishes to and/or should continue in the study.

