Per-Protocol Set (PPS)	All ITT participants without any major protocol deviations that could impact the primary endpoint.
Safety Analysis Set (SS)	All participants who receive at least one dose of study drug. Participants will be included into the analysis based on treatment actually received, regardless of the treatment randomized.

The ITT Analysis Set will be used for all efficacy and BL analyses except participant disposition which will be shown for the ITT Analysis Set and for the Safety Analysis Set if the two analysis sets differ. All randomized participants are expected to be dosed and any exceptions will be described in the CSR. The PP set will be determined prior to database lock and will be used as supplementary analyses of the primary endpoint. All safety analyses will be based on the Safety Analysis Set (SS).

2.21 *Statistical Analyses*

2.21.1 *General Considerations*

Statistical analyses will include tabulations of summary data, inferential analyses, by participant listings, and figures.

All statistical tests will be one-sided and will be performed at the 5% level of significance, unless otherwise stated. The vehicle control group will be combined for all efficacy analyses, and two-sided 90% confidence intervals will be presented. Frequency counts (n and percentages) will be made for each qualitative variable. Descriptive statistics (n, mean, standard deviation [SD], median, minimum, and maximum) will be calculated for each quantitative variable, unless otherwise stated. All data will be summarized by treatment group. All safety summaries and analyses will be based upon the Safety Analysis Set by treatment group (i.e., vehicle control doses (5% BID, 5% QID), vehicle control combined, active OTT166 doses (5% BID, 5% QID), and OTT166 combined).

The BL value for analysis and reporting will be based on the last (non-missing) measurement before dosing on Day 1. If any safety measurements are repeated after dosing on Day 1, then the last (non-missing) value of any repeated measurements will be used in the descriptive statistics and in the calculation of changes from BL.

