### 4.2 General Presentation Considerations

‘Baseline’ is defined as the last available pre-treatment assessment for safety assessments. For DRSS score, the Baseline value is defined as the Screening/Visit 1 result. Pre-treatment values for DRSS were collected at the Screening/Visit 1 using fluorescein angiography in addition to fundus photography whereas Baseline/Visit 2 used fundus photography only. Participants were enrolled into the study and randomized to the study treatment based on the Screening/Visit 1 DRSS result. All other efficacy analyses that do not use DRSS score will use the last available pre-treatment assessment as Baseline. If an assessment is taken on the same day as first administration of study drug, it is eligible to be used as the Baseline value. This is considered acceptable as this measurement is still the best representation of the Baseline value of the given assessment since it is highly unlikely that the study drug could have an impact on any measurement in a short period of time.

‘End of Study’ is defined as the last available post-treatment assessment.

‘Study Day’ will be calculated relative to the date of randomization for untreated randomized participants and relative to the date of first dose for treated participants. If event is prior to the first dose, then study day is calculated as:

$$\text{Date of Event} - \text{Date of Day 1.}$$

If event is after the first dose, then study day is calculated as:

$$\text{Date of Event} - \text{Date of Day 1} + 1.$$

‘Study day 1’ is defined as the date of randomization for untreated randomized participants or the date of first dose for treated participants.

Time to event analyses will be calculated from Study Day 1, including time to DRSS-related endpoints comparing to the Baseline value. These analyses will consider only post-Baseline assessments. The Visit 2/Baseline visit will not be considered.

Duration of Treatment (days) will be calculated as:

$$\text{Last Date of Dose} - \text{First Date of Dose} + 1.$$

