#### 4.11 Safety Evaluation

All safety summaries and analyses will be based upon the Safety Analysis Set by treatment group (i.e., vehicle control doses (5% BID, 5% QID), vehicle control combined, active OTT166 doses (5% BID, 5% QID), and OTT166 combined). Safety summaries for age, gender, race and ethnicity subgroups will be provided. If any safety measurements are repeated at the same visit after dosing on Day 1, then the last (non-missing) value of any repeated measurements will be used in the descriptive statistics and in the calculation of changes from BL. No inferential statistics will be performed for safety variables.

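### SAP 4.2 permits a same-day post-dose value to serve as Baseline for measures taken at Visit 2, contrary to the protocol's pre-dose rule and to the SAP's own pre-treatment wording

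*SAP*

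**What the plan says.** Protocol 2.21.1 (General Considerations) states: "The BL value for analysis and reporting will be based on the last (non-missing) measurement before dosing on Day 1". The Statistical Analyses part of the synopsis gives the same rule.

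SAP 4.2 gives three baseline rules and one allowance:

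- Safety: Baseline "is defined as the last available pre-treatment assessment for safety assessments".
- DRSS: "For DRSS score, the Baseline value is defined as the Screening/Visit 1 result".
- Other efficacy measures: "All other efficacy analyses that do not use DRSS score will use the last available pre-treatment assessment as Baseline".
- Allowance: an assessment "taken on the same day as first administration of study drug, it is eligible to be used as the Baseline value". The reason given is that "it is highly unlikely that the study drug could have an impact on any measurement in a short period of time".

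SAP 4.11 adds a rule for repeats, which begins "If any safety measurements are repeated at the same visit after dosing on Day 1, then the last (non-missing) value". That value then enters the descriptive statistics and the changes from baseline.

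SAP 4.14 and the rationale in SAP 6.3 say that the SAP overrides the protocol where the two differ.

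**The concern.** A value known to precede the first drop needs no argument about how fast the drug acts. The argument in SAP 4.2 is needed only if the same-day value may follow the dose. The allowance therefore departs from the protocol and from the word pre-treatment in the sentences before it. Because the SAP takes precedence, the looser rule is the one likely to be programmed.

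If a participant has a Day 1 record from after the first drop and it is the last one available, it can replace the pre-dose value. Any acute effect then sits in the reference, and later changes are measured from the wrong point.

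The general claim that no measurement can be affected also sits badly with the protocol. Section 2.14.10.2 plans for "Occurrence of hypersensitivity after instillation of the eye drops". Section 2.18.6 lists a fast pulse among hypersensitivity symptoms. The schedule of activities has the cornea checked for toxicity. The protocol thus allows for acute effects on some of the measures that take a Day 1 baseline.

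**Working it through.** The documents give no figure on this point: neither how often a Day 1 value is post-dose nor how large an acute shift might be. The one design figure, 66 completers per group, reproduces with the continuity-corrected formula (rates 0.06 and 0.26, one-sided alpha 0.05, 90% power). It concerns DRSS response and does not depend on this rule. The check is therefore mainly a comparison of the texts.

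**Step 1. Which measures can take a Day 1 baseline?** From the schedule (Protocol 2.15.1) and SAP 4.2:

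| Measure | Source of baseline | Exposed? |
|---|---|---|
| DRSS (primary efficacy) | Screening/Visit 1 by SAP 4.2 | No |
| Laboratory tests | Visit 1; samples must precede study drug (footnote i) | No |
| FA, OCTA | Scheduled at Visits 1 and 8 | No |
| TEAEs (primary safety) | Onset at or after Day 1 dosing (SAP 4.11.1); no baseline value used | No |
| Vital signs, IOP, slit lamp, cornea | Examined at Visit 2 | Yes |
| BCVA, SD-OCT (CST, macular volume) | Examined at Visit 2 | In principle |

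**Step 2. Is the order relative to the first drop fixed elsewhere?** For laboratory samples, yes. For the Visit 2 examinations the schedule states no order relative to the first drop. BCVA and CST have an indirect safeguard: the synopsis requires their limits to be met at the baseline examination, and eligibility review and randomization both fall at Visit 2. Those readings should therefore precede the first drop.

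**Step 3. Is a post-dose Day 1 assessment planned?** No. The schedule has one Visit 2 set. A post-dose Day 1 value could arise only as an unscheduled or repeat record.

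**Step 4. How would the SAP classify such a record?** Under 4.2 it is a same-day value and may be Baseline. Under 4.11 a safety repeat after dosing feeds the changes from baseline, which implies that it is post-baseline. The phrase in 4.11 may mean Day 1 itself or any visit once dosing has begun. On the first reading one record fits both rules, and the SAP does not say which prevails. Protocol 2.21.1 has a similar repeat rule but no such conflict, because its baseline must be pre-dose.

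**Step 5. What would the error be, given assumptions?** Let a share *f* of an arm have a baseline moved by *s* units. The error in that arm's mean change is −*f* × *s*. With assumed *f* from 0.05 to 1 and *s* from 1 to 5 units:

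- smallest: −0.05 × 1 = −0.05 units
- largest: −1 × 5 = −5 units
- *f* = 0: no error

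The error in an active-minus-vehicle difference in raw mean change is −(*f*₁*s*₁ − *f*₀*s*₀). It cancels if both arms are affected alike.

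An invented single case shows the mechanism. Pulse is 72 before the first drop, 110 after it and 75 at Week 4. The protocol rule gives 75 − 72 = +3. The post-dose baseline gives 75 − 110 = −35.

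**The case against.** The strongest reply is that the sentence is a harmless convention. It says eligible, not mandatory, and the governing definition is still the last pre-treatment value. It may be meant only for same-day records without a clock time, for which some convention is needed. With no post-dose Day 1 set scheduled, the practical effect may be nil. The repeat rules in Protocol 2.21.1 and SAP 4.11 are conditional and concern safety measurements only, so a BCVA retest after a drop is not foreseen anywhere.

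Most of this stands and limits the point. It does not remove it, because the SAP does not confine the allowance to untimed records and the stated reason covers known post-dose values.

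A reader might infer more, in three ways that the documents do not support:

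- *That a first-dose reaction vanishes from every change from baseline.* Step 1 shows that DRSS, laboratory, FA and OCTA changes are outside the rule. A reaction reported as an adverse event is still a TEAE, hypersensitivity is an AESI with 24-hour reporting, and SAP 4.11.3 lists repeated and unscheduled vital signs.
- *That BCVA change, the letter categories and the rescue endpoint are biased.* The eligibility check at Visit 2 points to pre-dose readings, and the BCVA rescue criteria (Protocol 2.14.9) also require new or increased central fluid.
- *That the bias favours the active arms.* This needs an acute effect specific to the drug and in a known direction. The documents give no evidence of either. It is plausible that repeats cluster in participants who reacted, but nothing in the documents establishes it.

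**Conclusion.** The point holds in limited form. SAP 4.2 contradicts Protocol 2.21.1 and its own pre-treatment wording. It yields a wrong reference value whenever a known post-dose Day 1 record is the last available one and the allowance is applied. This matters mainly for vital signs, IOP and slit-lamp or cornea findings, and only in principle for BCVA and CST. The overlap with SAP 4.11 is a second, smaller ambiguity.

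The size and direction cannot be derived from the documents. The range in the working rests on assumed shares and shifts, and the effect is zero if no post-dose Day 1 record exists. Neither the primary efficacy analysis nor the primary safety count depends on it. It is worth correcting before database lock because the conflict is plain and the repair is small.

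**What to change.** Revise SAP 4.2 as follows:

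- For all measures other than DRSS, Baseline is the last non-missing assessment before the first dose.
- A Day 1 record qualifies if its recorded time precedes the first dose or, where no time is recorded, if it belongs to the scheduled Visit 2 examination.
- A Day 1 record known to be post-dose is post-baseline. SAP 4.11 should refer to this rule, so that no record has two roles.
- Delete the justification about the drug being unlikely to act in a short time.
- Flag Day 1 values whose order relative to the first dose cannot be established.
- Keep Screening/Visit 1 as the DRSS baseline.

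The cost is one SAP paragraph and a filter in the baseline derivation, with no new data. Some timing is already collected: Protocol 2.16.8 has the time of day of IOP recorded, and TEAEs are classified by onset date and time. The downside is that a few participants may fall back to an earlier pre-dose value, such as the screening measurement.

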#### 4.2.1 Handling of Incomplete Dates

Every effort will be undertaken to avoid any missing or incomplete data. If variables are imputed, the analysis dataset will contain a new variable with imputed value and the original variable will contain the original missing value.

Inevitable partial dates will be imputed for start/end dates of AEs or concomitant medications.

##### Partial AE Start Date

- If only day is missing, then it will be set to:
  - First day of the month that the AE occurred, if month/year of the AE start date is different than the month/year of the first dose date.
  - The day of first dose date, if month/year of the AE start date is the same as month/year of the first dose date and month/year of the AE end date is different.
  - The day of first dose date or day of AE end date, whichever is earliest, if the month/year of the AE start and month/year of the first dose date and month/year of the AE end date are the same.
- If only month is missing, then it will be set to the earliest of the following:
  - January, as long as this date is after the first dose date
  - Month of the first dose date, if this date is the same day and year that the AE occurred
- If the day and month are both missing, then it will be set to the earliest of the following:
  - January 1 of the year, as long as this date is after the first dose date
  - Month and day of the first dose date, if this date is the same year that the AE occurred
  - The AE end date
- If dates are completely missing, then no imputation will be made.

##### Partial AE End Date

- If only day is missing, then it will be set to the earliest of the last follow-up date, last day of the month, or the date of death.
- If only month is missing, then it will be set to the earliest of the last follow-up date, December, or the date of death.
- If year is missing or AE is ongoing, the end date will not be imputed.
- If dates are completely missing, then no imputation will be made.

If the imputed AE end date is before the corresponding AE start date, then the AE end date will be set to the AE start date.

The same rule above will be applied to the start and end dates of concomitant medications.

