#### 4.8 Rescue Therapy

Participants meeting one or all the following criteria in the study eye would qualify for rescue with anti-VEGF therapy and/or PRP laser after consultation with the Medical Monitor:

Objective Rescue Therapy Criteria:

- Worsening DRSS level to 65 or higher as determined by the central reading center
- Decrease in BCVA of  $\geq 10$  ETDRS letters from BL associated with presence of new fluid or an increase in fluid in the central subfield compared to baseline at any visit
- Decrease in BCVA of 5 to 9 ETDRS letters from BL at two consecutive visits 4 weeks apart associated with presence of new fluid or an increase in fluid in the central subfield compared to baseline
- Increase in CST of  $\geq 75$  microns from BL associated with presence of new fluid or an increase in fluid in the central subfield compared to baseline
- Development of anterior segment neovascularization (ASNV)

Subjective Rescue Therapy Criteria:

- Any other condition that, in the clinical opinion of the investigator, warrants rescue therapy after consultation with the Medical Monitor

Summary tabulations of number and percentage of participants with rescue therapy, reasons for rescue and type of rescue therapy will be provided.

A by-participant listing will be provided.

The start date of rescue therapy in the study eye will be determined by the earliest concomitant medication in the study eye with ATC4CD="SL01A" or the earliest ocular concomitant procedure confirmed by the clinical team to be rescue therapy. This will be subset on the participants who have completed the "Rescue Therapy for Ocular Diabetic Complications" eCRF.

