The time to event secondary endpoints will be defined as time to first development of an event and will be estimated based on the Kaplan-Meier method, along with a 90% confidence interval. Analyses will be based on observed data, where participants who receive rescue medication will be censored at the start of rescue medication. A stratified log-rank test adjusting for the randomization stratification factor will be performed, to compare the combined vehicle control with each treatment group. Additionally, a stratified Cox proportional hazards model adjusting for the randomization stratification factor will be employed to estimate the hazards ratio between the combined vehicle control and each treatment group.

Continuous secondary endpoints involving change from BL to Week 24 will be analyzed using an analysis of covariance (ANCOVA) model with BL measurement of the variable as a covariate and treatment group and the randomization stratification factor as fixed factors. As a sensitivity analysis of the continuous secondary endpoints involving change from BL to Week 24, a rank-based ANCOVA model will be employed. The pair-wise comparisons of each OTT166 dose group versus combined vehicle control will be done in the ANCOVA model. Two-sided 90% confidence intervals for the difference of each OTT166 dose group minus combined vehicle control will be calculated.

The specific reasons for meeting rescue criteria as described in protocol section 2.14.9 will also be summarized using number and percentage by treatment group.

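### The adverse-event partial-date rule, carried over to rescue drugs, can date a rescue before the assessment that triggered it and so censor the triggering event

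*SAP*

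**What the plan says.** SAP 4.2.1 sets the scope of date imputation: "Inevitable partial dates will be imputed for start/end dates of AEs or concomitant medications". For a start date with only the day missing, the adverse-event rule has two main branches:

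- Outside the first-dose month: "First day of the month that the AE occurred, if month/year of the AE start date is different than the month/year of the first dose".
- Inside it: "The day of first dose date, if month/year of the AE start date is the same as month/year of the first dose date". If the event also ended in that month, the end date is used when it is earlier.

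After the end-date rules comes the carry-over: "The same rule above will be applied to the start and end dates of concomitant medications".

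SAP 4.8 then uses the medication record: "The start date of rescue therapy in the study eye will be determined by the earliest concomitant medication in the study eye". It identifies that record by ATC code. A rescue procedure confirmed by the clinical team is the alternative source.

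SAP 4.10.3, in line with 4.10.1.2, states that "participants who receive rescue medication will be censored at the start of rescue medication". SAP 4.10.2 also uses the rescue date. The observed-case analysis sets data after rescue to missing, and the LOCF analysis carries forward the last value before rescue.

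**The concern.** Early imputation is cautious for an adverse event, because it avoids missing a treatment-emergent onset. It is not cautious for a censoring date. There, an early date can remove the event that led to the rescue.

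Example: an eye is graded DRSS 65 at a visit on 5 May, and the injection is recorded as May with no day. The rescue start becomes 1 May, and the eye is censored event-free four days before its event.

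The trial's own data can show that such a date is wrong. Footnote e to Table 1 in Protocol 2.15.1 requires fundus photography and angiography after worse-than-mild PDR, ASNV or new or worsening CI-DME is diagnosed and before rescue. For those triggers a lower bound on the rescue date is on file, and the rule ignores it.

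Four secondary endpoints are exposed: time to worse-than-mild PDR, time to CI-DME, their composite, and time to objective rescue criteria. Events would be undercounted in whichever arm has more affected rescues. In the LOCF analysis the last visit before rescue can be dropped. In the observed-case analysis this matters when the dropped visit is Week 24 itself.

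**Working it through.** **The plan's design figure.** SAP 4.13 gives 66 per group for at least 90% power, with rates 0.26 and 0.06, one-sided alpha 0.05 and a continuity-corrected chi-square test.

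- Power = Φ[(d − 1/n − z·s0)/s1].
- d = 0.20, n = 66, z = 1.645.
- s0 = √(2 × 0.16 × 0.84/66) = 0.0638.
- s1 = √((0.26 × 0.74 + 0.06 × 0.94)/66) = 0.0614.
- Result: Φ[(0.20 − 0.0152 − 0.1050)/0.0614] = Φ(1.30) = 90.3%.
- Attrition of 5%: 66/0.95 = 69.5, so 70.

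The figure reproduces, and nothing below depends on it.

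**Inputs for the date check.** The missing-day rule comes from SAP 4.2.1. Visits at Weeks 4 to 24 with a ±7-day window come from the Schedule of Activities. The gap L from trigger visit to rescue is not in the documents, so it is an assumption, varied from 0 to 28 days.

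**Formula.** Outside the first-dose month the rescue is dated to the 1st. A rescue on day r of the month has its trigger at day r − L. The trigger falls after the imputed date when r − L > 1, that is, when r ≥ L + 2. Over a 365-day year with rescue equally likely on any day:

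share lost = Σ over months of max(0, days in month − L − 1) / 365

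- L = 0: (7 × 30 + 4 × 29 + 27)/365 = 353/365 = 96.7%
- L = 7: (7 × 23 + 4 × 22 + 20)/365 = 269/365 = 73.7%
- L = 14: (7 × 16 + 4 × 15 + 13)/365 = 185/365 = 50.7%
- L = 28: (7 × 2 + 4 × 1 + 0)/365 = 18/365 = 4.9%

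The mean back-dating is (7 × 465 + 4 × 435 + 378)/365 = 5,373/365 = 14.7 days.

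**Full enumeration.** This used 730 first-dose dates × 6 visits × 15 window days = 65,700 cases per gap, with the first-dose-month branch included:

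| Gap, trigger to rescue (days) | Trigger falls after imputed rescue date |
|---|---|
| 0 | 96.7% |
| 1 | 93.4% |
| 3 | 86.9% |
| 7 | 73.7% |
| 14 | 50.8% |
| 21 | 27.8% |
| 28 | 4.9% |

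In about 3% of cases the trigger falls on the imputed date itself. The first-dose-month branch covers at most 1.8% of cases. If the gap is instead spread evenly over 0–7, 0–14 or 0–28 days, with trigger visits at Weeks 4 to 20, simulation gives 85.2%, 73.7% and 50.3%.

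**With a floor at the trigger assessment.** The imputed date is never before the trigger, so the share lost is 0% at every gap, provided a tie counts as an event. Sample size and power do not change.

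**The case against.** The strongest reply is that the precondition hardly occurs. Rescue is given after consultation with the Medical Monitor, has its own eCRF, follows required imaging and ends study drug. Its date is easy to query, and the SAP imputes only partial dates that cannot be avoided. That stands: few records are expected.

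A reader might infer that every missing-day rescue loses its event. The documents do not support that:

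- The trigger must fall later in the same month than the imputed day. Central reading and the consultation lengthen the gap, so 96.7% is the upper extreme.
- A subjective rescue may have no qualifying event. CI-DME may have been recorded at an earlier visit, and an event dated before the imputed rescue start survives under the usual event-first reading.
- SAP 4.2.1 names only adverse events and medications, so a laser rescue recorded as a procedure is not clearly reached. A partial laser date has no stated rule.

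A reader might also infer that the primary endpoint is at risk. Under SAP 3.2.2, rescue before the Week 24 grading is non-response whatever its exact date. Only a rescue after the Visit 8 photographs, back-dated before them, would change the result, and Visit 8 is the end of study.

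Finally, a drug with only a pre-study start year takes its stop date as its start. A reader might infer that it is then misclassified. Under SAP 4.7 its prior or concomitant status does not change, the original value is kept, and nothing says imputed dates drive the deviation review.

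The pre-unmasking data review (SAP 4.4.1) is a real safeguard, but it states no check that rescue follows its trigger. The exception in SAP 4.10.2 for improvement before rescue is not repeated for the secondary time-to-event endpoints. It would not help once the imputed date precedes the event.

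**Conclusion.** The point holds as a conditional, minor defect in the text. For a drug rescue with a missing day, the SAP can assign a start that the trial's own visit data show is too early, and the triggering event can then be censored in four secondary time-to-event endpoints. Given a missing day, loss is likely at gaps up to about a week, about even at two weeks and rare at four. These shares rest on assumed gaps and on rescue being equally likely on any day of the month. The documents give neither the gap nor the frequency of missing days, so the number of participants affected cannot be computed. No effect on the primary endpoint is shown beyond the Visit 8 edge case.

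**What to change.** Keep the existing rule for other concomitant medications and make three additions before database lock:

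1. In SAP 4.2.1 or 4.8, add an override for study-eye rescue medications and procedures. A partial start date is imputed as the later of the 1st of the recorded month and the date of the study-eye assessment that triggered rescue. For subjective rescue, use the visit at which the rescue decision was recorded.
2. In SAP 4.10.1.2 and 4.10.3, state that an event on or before the rescue start counts as an event. Without this, the floor only turns losses into ties.
3. As a minor addition, when only the start year is known and it precedes the first-dose year, impute 1 January of that year and not the stop date. This mainly affects the exploratory fellow-eye LOCF analysis in SAP 4.10.4.

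The cost is about one SAP paragraph and a small programming change, with no new data.
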